Consent. The following two-step consent process will occur within the Tula app on the patient subject's smartphone. After the individual has downloaded the app, they will be presented with Informed Consent #1, which requests their broad consent for the study. This consent includes detailed information applicable to all participants in the study, regardless of randomized group

Protocol

HS IRB #2019-0337
Version 5. 10/17/19
Version 6. 04/07/20
Version 7. 10/09/20
Version 8. 01/26/21
Version 9. 08/18/21
Version 10. 07/13/23

assignment, and a step-by-step process overview of their activities—including their immediate next steps for completing their enrollment (comprised of the 72-hour run-in and Consent #2). Upon completing Consent #1, participants will be asked to create a Tula account. Once created, they will be asked to complete the items on the Quick Start Checklist. Patients who do not complete the checklist tasks will not be randomized and all collected data (except age, biological sex, and reason for ineligibility) will be destroyed. Age, biological sex, and reason for ineligibility will be kept for generalizability and reporting reasons. Randomization (see below) occurs after patients complete the checklist tasks during the 72-hour run-in period.

The research team will use the private messaging feature in Tula to schedule a phone call with individuals who remain in the study. During that call, a member of the research team will confirm the participant's consent, answer any additional questions about the study that the patient has, and will randomize the individual to one of three groups of Tula users. Once randomized, patients will be prompted to complete Informed Consent #2 via the app, the next time they login. Informed consent #2 serves as an addendum to Consent #1 and provides detailed information specific to the patient's assigned group.

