Patients are advised to take their time reading the consent forms; they may leave and return to them and reread sections if they'd like to. To mitigate any potential difficulties related to readability (i.e. length of the document, screen size, small text) and to ensure participants understand the most critical aspects of their participation in the study, we will preface the full text of the consent form with a bulleted list, highlighting in plain language the following sections: what the study is about, how we will protect their confidentiality, benefits and risks involved, remuneration, voluntary nature of participation, their participation and their healthcare, and contact information for questions. Subjects will also be able to listen to a verbatim recording of each consent form using a screen reader. If the subject has not agreed to the informed consent after two weeks, he or she will no longer be able to join the study and all data collected during the screening process will be destroyed (except age, biological sex, and reason for exclusion, per CONSORT standards). A copy of the consent form will be accessible to the study coordinator via the Tula server. Subjects can refer to the consent forms electronically by navigating to the Study Information sections of Tula. They will also be able to email the consent form to themselves. If a subject declines to participate at any time during the consent process, he or she may select a "I choose to not participate" button that will ask them why and return them to the launch screen. Reasons for refusal will be noted, in line with CONSORT standards.⁵⁷ Subjects who choose not to disclose why they are ending their participation in the study will also be able to say "I choose not to respond" or "none." All subjects will be reminded that they are under no obligation to participate in this study and can withdraw from the study at any time. They are also told that their health care will not be affected by their participation in this study. Once subjects opt out of the study, they will no longer have access to Tula.

Randomization. Randomization will be done by the study coordinator using the urn randomization program and happen prior to informed consent #2. Study staff will access the admin tool within Tula to assign patients to the self-monitoring, peer-supported, or clinically integrated groups. Randomization will be done in block randomization by clinic, sex, and severity of alcohol use.

Protocol

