HS IRB #2019-0337
Version 5. 10/17/19
Version 6. 04/07/20
Version 7. 10/09/20
Version 8. 01/26/21
Version 9. 08/18/21
Version 10. 07/13/23

Following randomization, study staff will call the individual to notify them which group they are in and explain what is required of them.

Patients will need to install just one version of Tula because the features patients have access to will be modified according to the randomization group.

Patients in all groups will be asked during the consent process to allow monitoring of their Tula usage by the research team to determine which parts of Tula are most helpful; patients randomized to the clinically integrated group will have the option to share information from Tula with the health coach at UW Health. All data shared from patients to the UW Health health-coach will be initiated by the patient.

Remuneration. Participants who complete the screening survey will receive a \$10 digital Amazon.com Gift Card in the email sent to communicate their eligibility status, regardless of their eligibility.

In all recruitment scenarios, subjects will be told the study incentives (\$10 for completing the eligibility screen; up to \$250 for enrollment and participation in the study) and how to earn them in the study:

- complete baseline measures in the Tula app, for which subjects will be paid \$30;
- complete weekly surveys for the first 12 weeks of the study, for which subjects will be paid \$10 per completed week (all groups);
- complete 4 quarterly surveys (between months 3-12), for which participants will be paid \$20 each;
- earn a bonus of \$20 for completing all surveys

Incentives will be distributed monthly to subjects by digital gift code. If subjects prefer to receive incentives via e-mail, they must grant the study team permission to use their email address for this purpose; otherwise, monthly incentives will be delivered securely through the in-app communication tool (private message). Subjects will be notified of this information when they formally consent to participate in the study

For the participant interviews, each participant will receive a \$50 gift card in remuneration for their time.

Clinic Staff

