6.0 MEASUREMENT OF EFFECT

All scales have good psychometric properties with similar populations. Listed below are the factors to be measured and measurement instruments.

Intake only. Study staff will confirm patient eligibility via patients' UW Qualtrics screening surveys . Patients report demographics (biological sex, race, ethnicity, age, education).

Protocol
HS IRB #2019-0337
Version 5. 10/17/19
Version 6. 04/07/20
Version 7. 10/09/20
Version 8. 01/26/21
Version 9. 08/18/21
Version 10. 07/13/23

Drinking and quality of life. Patients will be asked to take surveys administered via the Tula app (see Table 1 for frequencies). Patients will be asked to report on their drinking using the 7-day timeline follow-back^{58,59} survey. Patients will also take the PROMIS Global Health⁶⁰ survey (10 items) to assess patient self-reported quality of life and a modified version of the Brief Alcohol Monitor⁶³ survey (10 items) to assess their risk and protection factors for problematic alcohol use. Alcohol use disorder severity (AUD scale,⁶⁴ 11 items; AUDIT, 10 items; 7-day timeline followback, 5 items) will be assessed at baseline and once every 3 months.

Mediators. Self-determination theory constructs will be assessed (see Table 1 for frequencies) via the Tula app as follows:

- Competence – Perceived Competence Scale (4 items)
- Relatedness – CHESS Bonding Scale^{65,66} (5 items)
- Autonomous motivation – revised Treatment Self Regulations Questionnaire⁶⁷ (6 items)

Tula use. Tula use is collected in time-stamped log files and includes when a patient accessed Tula, the services used, duration of service use, pages viewed, messages posted and received, and content of messages. Tula use will be used to measure dose of intervention received for dose/response analyses. Patients will be asked to take a survey about their value of Tula at baseline and 12 months.

Healthcare utilization. Healthcare utilization will be collected from the self-reported medical services utilization form⁶¹ (6 items; see Table 1 for frequency).

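### Arm-specific Consent #2 comes after the arm is known, and the only decline option described at that step also ends the in-app outcome surveys, so follow-up loss can differ by arm

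*Combined protocol and SAP*

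**What the plan says.** All references are to the combined protocol and SAP.

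- **Before randomisation.** Consent #1 (broad consent) and the Quick Start tasks of the 72-hour run-in, including the baseline survey, come first (sections 4.0 Consent and 5.0). On a scheduled call, staff confirm consent and randomise.
- **Order.** Section 4.0, Randomization: "Randomization will be done by the study coordinator using the urn randomization program and happen prior to informed consent #2".
- **Arm disclosed.** "Following randomization, study staff will call the individual to notify them which group they are in and explain what is required of them".
- **Consent #2.** "Once randomized, patients will be prompted to complete Informed Consent #2 via the app, the next time they login". The form "provides detailed information specific to the patient's assigned group". The process overview in Consent #1 lists "their immediate next steps for completing their enrollment (comprised of the 72-hour run-in and Consent #2"), so Consent #2 is treated as part of enrolling.
- **Declining.** "If a subject declines to participate at any time during the consent process, he or she may select a" button stating that they choose not to take part, which asks for a reason and returns them to the launch screen. "Once subjects opt out of the study, they will no longer have access to Tula".
- **Outcomes.** Section 6.0, on drinking and quality of life: "Patients will be asked to take surveys administered via the Tula app (see Table 1 for frequencies"). Section 8.0 (Quantitative data collection) likewise has the patient surveys collected by the Tula system.
- **Analysis.** Section 8.0 names intention-to-treat, as-treated, per-protocol and complier-average analyses, with pattern-mixture modelling for missing data. It does not say how a patient who is randomised and then declines Consent #2 is handled.

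**The concern.** Randomisation protects the comparison only while everyone randomised can be followed. Here a patient first learns the arm and is then asked to agree to it. What is being agreed to differs between arms: the self-monitoring group has no discussion group, the peer-supported group has one with a peer moderator, and the clinically integrated group also has a health coach with up to three sessions, the first lasting 60 to 90 minutes (sections 1.0 and 5.0). Reasons for declining may therefore differ by arm. A patient who declines has month-0 data and no later drinking or quality-of-life data. If the share declining, or the kind of patient who declines, differs between arms, the between-arm contrast is biased. The run-in removes poorly engaged patients beforehand, but it cannot screen for reactions to an arm that has not yet been assigned.

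**Working it through.** **1. The sequence.** Section 4.0 does not expressly place the notification call before the Consent #2 screen. That does not matter, because the form is itself arm-specific: whoever decides on Consent #2 knows the arm. Declining means leaving the study; leaving ends Tula access; the surveys are in Tula. No other route for follow-up data is described for such a patient.

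**2. What the planned analysis can do.** Pattern-mixture modelling borrows from what each missing-data pattern has observed. A pattern with month-0 data only contains nothing about later drinking, so its follow-up values must be assumed.

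**3. Size.** The plan has no figure for this step to reproduce. Its relevant figures (section 8.0, Power) are 182 patients per group, d=0.23 stated as equal to 1.37 risky drinking episodes per month, and 23% overall attrition. The implied SD is 1.37/0.23 = 5.96 episodes per month. The share lost, f, and the difference between lost and retained patients, k (in SD), are assumptions.

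The mean of all patients in an arm is (1−f) × retained mean + f × lost mean. It therefore differs from the retained mean by f×k. Between two arms the unadjusted bias is f₁k₁ − f₂k₂.

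| Assumed loss | k | Bias (SD) | Share of 0.23 | Episodes/month (× 5.96) |
|---|---|---|---|---|
| 5% in one arm | 0.25 | 0.05×0.25 = 0.0125 | 5% | 0.07 |
| 10% vs 5% | 0.5 | 0.05−0.025 = 0.025 | 11% | 0.15 |
| 10% in one arm (18 of 182) | 0.5 | 0.10×0.5 = 0.05 | 22% | 0.30 |
| 15% in one arm | 0.5 | 0.15×0.5 = 0.075 | 33% | 0.45 |
| Equal in both arms, same k | any | 0 | 0% | 0 |

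**4. Effect of baseline adjustment.** The plan adjusts for baseline outcome. If a share s of the difference k is carried by baseline drinking, about f×k×(1−s) remains. A simulated ANCOVA (2,000,000 per arm, 10% lost from one arm, k=0.5, baseline-outcome correlation 0.5 or 0.7) agrees to within simulation error: about 0.05 SD for s=0, 0.024 to 0.025 SD for s=0.5, and essentially 0 for s=1.

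**The case against.** The strongest reply is that this is ordinary withdrawal. Any subject may leave at any time, and opting out ends Tula access whenever it happens; Consent #2 is an addendum to a broad consent already given and reconfirmed by phone. That largely stands: Consent #2 adds a prompted exit point to an existing risk and does not create the risk.

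A reader might infer that a patient cannot refuse the arm's features and stay in follow-up. The documents do not support that. Coach sessions are encouraged, not required; data sharing is a yes/no choice at each survey and can be revoked; the discussion group is access, not an obligation (sections 1.0 and 5.0, including Privacy and Confidentiality). A patient in the study can leave these unused and still answer surveys. The gap is narrower: no survey-only choice for someone who declines Consent #2.

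A reader might also infer that merely leaving Consent #2 unsigned ends access, or that the two-week data-destruction rule in section 4.0 reaches randomised patients. The text says neither; the rule reads more naturally as applying to Consent #1.

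It is also fair that f, k and one-sided loss are assumed. All arms share the same static content and the described survey payments do not vary by arm, which reduces reasons to leave. Loss of 10% to 15% at this one step would be 43% to 65% of the plan's 23% total attrition (10/23, 15/23), so the upper values are demanding. Reasons for refusal are already recorded, though reporting by arm is not specified.

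Finally, turning Consent #2 into an information sheet would not by itself retain outcomes from patients who leave after hearing their arm. That is correct, and is why the fix has two parts.

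**Conclusion.** The concern holds in limited form. The order of steps adds a formal, arm-specific decision after allocation, and the only decline option described there ends outcome collection. Loss can therefore differ by arm; nothing shows that it does.

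The size cannot be determined from the documents. The illustrative range is 0.0125 to 0.075 SD (5% to 33% of d=0.23) before baseline adjustment, resting wholly on assumed f and k. It is zero if equal shares are lost with the same difference in each arm, or if baseline drinking carries the whole difference.

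It would be too strong to conclude that intention-to-treat is impossible: consent, run-in and baseline precede randomisation, so everyone randomised can be identified by arm. It is weakened because some would have no follow-up values. Priority is minor to moderate.

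**What to change.** Two parts, both needed.

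1. **Complete consent before allocation.** Give the arm-specific information for all three groups, and obtain all consent, before randomisation, for example in Consent #1 or on the existing call before the patient is randomised. Consent #2 then stops being a decision point. The consent forms are not in the copy reviewed; if Consent #1 already describes the arms, only the status of Consent #2 needs to change.
2. **Separate stopping from withdrawing.** Patients can still leave after learning their arm. Distinguish stopping Tula or the arm's features from withdrawing from data collection. Offer those who stop but agree to follow-up the quarterly surveys through a survey-only app setting or, with permission, a Qualtrics link, as IRB terms allow. The Qualtrics screening survey already supplies the baseline timeline follow-back, AUDIT and DSM-5 data (section 5.0, Baseline survey).

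In section 8.0, define intention-to-treat as everyone randomised, analysed as assigned, and report post-randomisation declines by arm. As a minor clarification, state which consent the two-week rule covers.

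**Cost.** An IRB wording change, a somewhat longer consent before randomisation, and an app setting or survey link. Survey payments are up to 4 × $20 = $80 per retained patient. At an assumed 10% of an arm (18 patients) that is 18 × $80 = $1,440, within the $250 per patient already planned (30 + 12×10 + 4×20 + 20). If enrolment is too advanced to reorder consent, part 2 and the reporting changes remain available.

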5.0 INTERVENTION PLAN

All patients enrolled in the study will participate in a 3-month intervention period followed by a 9-month follow-up period, for a total of 12 months. Patients are allowed to continue using Tula after the 12-month period, but will not be asked survey questions after 12 months. Please note that Tula is not a treatment—it is a resource used to help patients reduce their drinking.

All patient subjects will undergo a 72-hour run-in period when they will have access to the basic version of Tula. During this period, potential subjects will be asked to complete the Quick Start checklist items within the 72 hours. The checklist tasks are completing the baseline survey; setting goals for the 90-day active intervention period related to drinking and, optionally, to other aspects of health (e.g., sleep, exercise); completing the first weekly survey; and completing a survey called What Matters to Me, which helps patients think about their current health status and what they would like to change. After 72 hours, patient subjects who complete these tasks will be randomized to one of three groups and receive the appropriate access to Tula features.

Patients in all three groups—regardless of randomization group—will have access to the same static content on Tula, which is described in Section 1, Background and Significance. In addition, patients in all three groups will be asked to complete (1) a weekly survey during the active intervention period and, optionally, to revise the goals they set during the run-in period and (2) quarterly surveys at month 3, 6, 9, and 12. Subjects are free not to answer any survey questions.

Self-monitoring (control) group. Patients of this group will continue receiving regular care from their physician with no interference from the two experimental groups. No data will be shared with other participants. Only the research team will have access to subject data for evaluation purposes.

Peer-supported group. In addition to the static content available to patient subjects in all three groups, patient subjects in this group will have access to a discussion group where they can message one another and have the ability to share and see posts of other patients. The only involvement of someone other than patients themselves in the peer-supported Tula group will be by a trained peer mentor (i.e., a dedicated Tula user from the area with a sustained history of successful alcohol reduction). The peer mentor will participate in Tula discussion groups, moderate the discussions, and encourage use of the system (e.g., by posting topics in the discussion group, pointing Tula users to a potentially helpful tip). The peer mentor will not have access to individual Tula use data. Patient-reported feedback will be presented directly to the patient only. The peer mentor will be introduced to

Protocol

HS IRB #2019-0337
Version 5. 10/17/19
Version 6. 04/07/20
Version 7. 10/09/20
Version 8. 01/26/21
Version 9. 08/18/21
Version 10. 07/13/23

the study by the study coordinator and receive access to Tula for 36 months.

Two Certified Peer Specialists from Safe Communities of Madison-Dane County will provide participant mentoring and discussion forum moderation for the peer-supported group. These peer specialists, who will serve as peer mentors for the study intervention, completed the CITI Human Subjects Research Training: UW Biomedical Course using the materials and attestation form provided by UW's Human Research Protection Program (HRPP) and have been added to the IRB study record as external personnel.

Clinically integrated group. In addition to receiving the same static content available to all patients, patients in the clinically integrated group will also have access to a discussion group with others in the group (like the peer-supported group described above) and access to a health coach from the UW Health Wellness Center. Health Coaching at UW Health's Center for Wellness at the American Center is provided by a Certified Wellcoach, either in-person at the American Center or over the phone. Health Coaching sessions are not scheduled via Health Link: Health Coaches directly and independently manage their own client calendars. Patients schedule a session directly with the Health Coach via phone or email. When the Health Coach sees a client for more than one session, they schedule the first session via phone or email, then set up subsequent sessions during the first session. Standard clinical Health Coach appointments are not documented in any way in Health Link, nor will they be for this study; as an out-of-pocket, open-to-the-public service, The Center for Wellness uses an independent third-party system, ActiveNet, for any billing needs.

Patients will be encouraged to participate in up to three in-person or phone visits with the health coach at the beginning, middle, and end of the active 90-day implementation period, with the first visit lasting between 60 and 90 minutes and the other two lasting between 20 and 45 minutes. The health coach will also function as the moderator of the discussion group, as the peer mentor does in the peer-supported group.

Patients will have the option to share selected Tula data with the health coach through a dashboard. When a patient in this group completes a survey, they will be presented with a question: "Do you want to share your responses with the health coach? Yes/No." If the subject responds "yes," their survey responses will populate a dashboard that contains data on drinking days / drinks per day and other data reported via the weekly survey. The health coach will have the option to view the data in the dashboard. Data in the dashboard will not be placed in the patient subject's electronic medical record. However, if the health coach sees any data that is concerning that would normally prompt follow-up within the scope of their clinical role, the health coach will contact and follow-up with the patient subject if such a situation were to arise.

The UW Health Coach at the American Center is not professionally obligated to communicate with a patient's PCP; in most coaching circumstances, the Health Coach would not know the identity of a patient's PCP, and having an established relationship with a PCP is not a prerequisite for inclusion in

Protocol

HS IRB #2019-0337
Version 5. 10/17/19
Version 6. 04/07/20
Version 7. 10/09/20
Version 8. 01/26/21
Version 9. 08/18/21
Version 10. 07/13/23

the study or health coaching in general. That said, there may be circumstances where action/communication may be warranted if a subject discloses information that has a direct bearing on his or her health. The Wellness Center has several primary care providers on site at the American Center that the health coaches involved in this study routinely consult in such circumstances.

This sensitive health information being collected and shared through the Tula dashboard allows the coaches to be better informed and provide more responsive treatment. Information shared via the dashboard serves only to support the intervention and will not be used as study data; no response is expected of the health coach relative to her research role. Health coach communication with a patient in the course of the intervention will be dependent on the individual health coaching plan the patient creates with the support of the health coach in accordance with the Whole Health model used by the health coach. If a patient declines to share data to the dashboard, no data will be transmitted to the dashboard.

To schedule the first of three coaching visits, which may take place on-site at the UW Health Center for Wellness or via phone conversation, the health coach will use the private messaging feature in Tula. Subsequent visits may be scheduled during that first 60-90 minute visit or via the app's private messaging feature, depending on the patient's preference. During the consult, the health coach will review "What Matters to Me," the Wellness Center survey patients complete during the run-in period. The health coach will work with the patient to form a vision of what their health could be by asking the patient "What do you want your health *for*? ", helping the patient develop a short-term goal, and formulate an action plan. Following the initial coaching session, the patient may use Tula to journal about their experiences so they can refer to this information during brief weekly or bi-weekly follow-up encounters with the health coach, which will take place via private message over Tula, and/or during their two subsequent health coaching visits. The health coach will ask patients how they are doing, how they are progressing toward their goals, where they want to go from here, and how they want to get there. The health coach will provide structure for the patient to achieve their self-identified goals.

Clinic staff. Clinic staff will be asked to participate in interviews in a private room at their clinic. The study team will interview two groups of clinicians: 1) the primary care clinicians who the team interviewed in the developmental year and 2) clinicians at clinics that have had at least 10 patients (in the clinically integrated group) using Tula. Interviews will take place once the intervention phase of the study is complete. Clinic staff subjects will be informed of the study and sign an informed consent. Subjects will be reminded that their participation is voluntary, that they do not need to answer any questions they do not want to answer, and that they may leave the interview at any time. The study team will ask open-ended questions about the implementation process of Tula such as what barriers to implementation the clinic experienced, what worked well, and what can be improved upon for next time. Clinicians will also be asked the "Iowa A-CHESS value for clinic managers" survey. The interview will be recorded and transcribed by a member of the study team. During transcription all names will be coded and any identifying information will be removed.

Protocol

HS IRB #2019-0337
Version 5. 10/17/19
Version 6. 04/07/20
Version 7. 10/09/20
Version 8. 01/26/21
Version 9. 08/18/21
Version 10. 07/13/23

External Research Site and Personnel

Safe Communities of Madison–Dane County is a local non-profit [501(c)(3)] coalition that brings together public and private sector partners to save lives, prevent injuries, and make the community a safer place. The organization focuses on projects and programs with a track record of positive impact and success and has been involved with research projects and initiatives at UW–Madison and UW Health since its inception in 1999. As a community partner for this study, Certified Peer Specialists employed by Safe Communities will provide in-app peer mentoring and discussion forum monitoring/moderation for the study arm receiving the peer-supported intervention. Certified Peer Specialists recognized in the State of Wisconsin complete peer support training, examination, and continuing education requirements specific to both mental health and substance use-oriented lived experiences. Safe Communities of Madison–Dane County is accredited under guidelines established by the World Health Organization Collaborating Center on Community Safety Promotion, National Safety Council's Safe Communities America Network and Pan Pacific Network of Safe Communities.

Data collection.

Table 1 shows the data collection for the study, including source, burden, and timing.

Table 1: Quantitative Outcomes

Dimension	Measure	Source	Burden	Timing (after rand.)
Patient Outcomes				
Risky drinking patterns	Timeline followback ^{58,59}	Patient survey	5	0, 3, 6, 9, 12 mo.
Quality of life	PROMIS Global Health ⁶⁰	Patient survey	10	0, 3, 6, 9, 12 mo.
Willingness to share data	Number of participants opting to share Tula data with clinicians	Tula	NA	Continuous
Cost				
Healthcare utilization	Medical services utilization form ⁶¹	Patient survey	4	0, 6, 12 mo.
Implementation costs	Clinician experience with implementation of Tula.	Staff interview	60 min.	Once, after the intervention is complete.
Other Outcomes				
Risk/protection factors	Brief Alcohol Monitor ⁶³	Patient survey	10	0, 3, 6, 9, 12 mo.
Specialist report use (clinicians)	Number of days used	Server log files	NA	Continuous
Alcohol use severity	AUDIT	Patient survey	10	
AUD severity	DSM-5 ⁶⁴	Patient survey	11	Pretest, 12 months
Patient and clinician decision making	Value and decision framing survey	Patient/ clinician survey	9	Patient: Pretest, 12 months Clinician: during interview at month 36
Mediators				
Relatedness	CHESS Bonding Scale ^{48,65}	Patient survey	5	
Competence	Perceived Competence Scale	Patient survey	4	0, 3, 6, 9, 12 mo.
Autonomous motivation	TSRQ ⁶⁶	Patient survey	6	
Tula use (patients)	Number of days used, number of pages viewed	Server log files	NA	Continuous
Moderators				
Patient characteristics	Race, ethnicity, gender, age	Patient survey	NA	Pretest

Protocol

HS IRB #2019-0337
Version 5. 10/17/19
Version 6. 04/07/20
Version 7. 10/09/20
Version 8. 01/26/21
Version 9. 08/18/21
Version 10. 07/13/23

All survey data collected through Tula is housed on CHESS servers then exported to the UW sponsored Google Drive folder for statistical analyses.

Screening survey: People interested in participating in the study will be directed to take a Qualtrics screening survey hosted on the Web to determine if they are eligible to participate in the study.

Baseline survey. After patient subjects are enrolled in the study, they will be asked to take a baseline survey consisting of demographic questions, medical service utilization, quality of life, a modified version of the Brief Alcohol Monitor, the CHESS bonding scale, the alcohol competence scale, the TSRQ, and the value of Tula. Data from the screening survey will be used as baseline data for the AUDIT, AUD DSM-5, and timeline follow-back. Two additional questions related to the impact of COVID-19 on participants' physical and mental health will be added to the quality of life measures. These questions will operate on a 5-point Likert scale and will be included across all CHESS studies. (See supporting document "4.6.20 Global Health Scale v1.3_COVID.docx").

Quarterly follow-up surveys. Starting at month 3, patient subjects will be asked to take surveys once every 3 months. The study team will ask patient subjects to take the following surveys: 1) quality of life, 2) a modified version of the brief alcohol monitor, 3) timeline follow-back, 4) CHESS bonding scale, 5) alcohol competence scale, 6) TSRQ, 7) medical services utilization (6 months and 12 months only), 8) AUD severity (12 months only), 9) value of Tula (12 months only), 10) quality of life and 11) AUDIT. Two additional questions related to the impact of COVID-19 on participants' physical and mental health will be added to the quality of life measures. These questions will operate on a 5-point Likert scale and will be included across all CHESS studies. (See supporting document "4.6.20 Global Health Scale v1.3_COVID.docx").

Use data. The app automatically collects use data by placing "cookies" on subjects' smartphones (with patients' consent) when randomization takes place. Data are stored on a secure central server at CHESS.

Qualitative interviews. In order to better understanding the implementation of Tula in the health coaching and peer mentoring organizations, the study team will use the CFIR framework to interview the two health coaches and four peer mentors, as well decision makers in these organizations. In order to better understand the conditions under which Tula can be sustained, the team will conduct interviews with organizational decision makers and health system decision makers. Sample questions for each of these interviews are shown below. Interviews will take place at month 36 and last 30-60 minutes. Members of the research team who have received training in qualitative interviewing will conduct the interviews. Interviews will be conducted via a secure video conference call (Zoom) and will be audio recorded. Participant identities will be protected. Any identifiers will be coded in the transcripts so that there will be no way to link clinicians to their interview responses. Data collected will be used to refine the system for future dissemination.

Protocol

HS IRB #2019-0337

Version 5. 10/17/19

Version 6. 04/07/20

Version 7. 10/09/20

Version 8. 01/26/21

Version 9. 08/18/21

Version 10. 07/13/23

For health coaches and peer recovery workers	Sample Implementation Questions
CFIR Domain	
Inner Context	
How would you describe your role in Tula?
 
Please walk me through everything you did related to Tula.
 
Probe for both interpersonal (inc. discussion facilitation) and logistical work.
 
Probe for what worked well and what didn't relative to the interpersonal and logistical tasks.
 
Probe for what was gained and what was lost by doing everything virtually.
 
In what ways did your work on Tula fit well with your broader role here at [organization]?
 
In what ways was it a poor fit?
 
Is Tula's harm reduction philosophy consistent with the philosophy at [organization]? If yes, tell me more about how it is consistent? If no, tell me more about how that affected your work with Tula?
 
Thinking about [your organization], what do you have in place here that made it possible for you to do your Tula work?
 
What were the barriers?

Outer Context	Other than [things mentioned within organization that

Protocol

HS IRB #2019-0337
Version 5. 10/17/19
Version 6. 04/07/20
Version 7. 10/09/20
Version 8. 01/26/21
Version 9. 08/18/21
Version 10. 07/13/23

	
supported Tula], what helped Tula to be successful? And what got in the way of that success? How did the pandemic shape your experience? How did the pandemic affect the experience of people using Tula? Which users seem to benefit from Tula? What tells you this? What about users for whom it didn't seem to work?

Innovation	
I'm interested in learning about how you think about how people change. Specifically, please tell me what you understand about how people reduce their alcohol consumption? In what ways does Tula help people in reducing their alcohol consumption? In what ways does it fall short? How should Tula be changed to work better for folks in making this change?

Bridging	
Thinking about the Tula team [name individuals], what did they do that was most important to supporting you in working with Tula? What could be improved?

Protocol

HS IRB #2019-0337
Version 5. 10/17/19
Version 6. 04/07/20
Version 7. 10/09/20
Version 8. 01/26/21
Version 9. 08/18/21
Version 10. 07/13/23

For HC/PM decision-makers CFIR Domain	Sample Implementation Questions	Sample Sustainment Questions
Inner Context	
What is your role at [organization]?
 
What role did you play in implementing Tula at [organization]?
 
Thinking about [your organization], what do you have in place here that made it possible for you to implement Tula?
 
What were the barriers to implementation?
 
Is Tula's harm reduction philosophy consistent with the philosophy at [organization]?
 
If yes, tell me more about how it is consistent?
 
If no, tell me more about how that affected [organization's] implementation of Tula?
	
Who at [organization] would make the decision about making Tula part of your regular service offerings?
 
What would matter when making this decision?
 
What steps would need to be taken in order to make Tula part of your regular service offerings?
 
What would need to be in place at [organization] in order for you to make Tula part of your regular service offerings?

Outer Context	
Other than [things mentioned within organization that supported Tula], what helped [organization] to implement Tula?
 
And what made implementation difficult?
	
What would need to be in place external to [organization] in order for Tula to be made part of your regular service offerings?

Innovation	
What's your overall assessment of Tula?
 
What's the value of Tula?
 
• For users• For the work that you do here at [organization]	
How could Tula be improved to enhance [the value of Tula they have described]?

Protocol

HS IRB #2019-0337
Version 5. 10/17/19
Version 6. 04/07/20
Version 7. 10/09/20
Version 8. 01/26/21
Version 9. 08/18/21
Version 10. 07/13/23

Bridging	Thinking about the Tula team [name individuals], what did they do that was most important to supporting you in working with Tula? What could be improved?	What can the Tula team do now that would make it more likely that [organization] would make Tula part of its regular service offerings?
----------	--	---

For health system decision makers	Sample Sustainment Questions
CFIR Domain	
Inner Context	Who at [organization] would make the decision about making Tula part of your regular service offerings? What would matter when making this decision? What steps would need to be taken in order to make Tula part of your regular service offerings? What would need to be in place at [organization] in order for you to make Tula part of your regular service offerings?
